#### For Both Dose Escalation and Expansion:

• Must have acceptable laboratory parameters according to the table below:

Parameter	Result
Acceptable renal function	GFR ≥30 mL/min (estimated using Cockcroft-Gault formula, see Appendix 4)
Acceptable liver function	
- Bilirubin	Total bilirubin ≤3.0×ULN a
Acceptable hematological status	
- Hemoglobin	≥5.6 mmol/L (9.0 g/dL) b
- ANC	≥1500/µL (1.5×10  /L)
- Platelet count	≥100×10 °/L

ALT=alanine aminotransferase; ANC=absolute neutrophil count; AST=aspartate aminotransferase; GFR=glomerular filtration rate; ULN=upper limit of normal.

- a. Except in subjects with Gilbert's syndrome, then direct bilirubin \( \leq 2 \times ULN. \)
- b. Must be met without erythropoietin dependency and without transfusion within 2 weeks prior to C1D1.

Version: 4.0

[figure not shown]
#### **Key Exclusion Criteria**

- Has an uncontrolled intercurrent illness, including but not limited to:
  - Ongoing or active infection requiring intravenous treatment with antiinfective therapy that has been administered less than 2 weeks prior to first dose.
  - Symptomatic congestive heart failure (grade III or IV as classified by the New York Heart Association), unstable angina pectoris or cardiac arrhythmia.
  - O Has a marked baseline prolongation of QT/QTc interval (eg, repeated demonstration of a QTc interval >480 milliseconds (ms) (CTCAE grade 1) using Fridericia's QT correction formula.
  - O Uncontrolled hypertension defined as systolic blood pressure ≥160 mmHg and/or diastolic blood pressure ≥100 mmHg, despite optimal medical management.
  - Ongoing or recent (within 1 year) evidence of significant autoimmune disease that required treatment with systemic immunosuppressive treatments, which may suggest risk for immune-related adverse events (irAEs). Note: The following conditions are not exclusionary: Childhood asthma that has resolved, residual hypothyroidism that required only hormone replacement or psoriasis that does not require systemic treatment.
  - Subjects with a history of grade 3 or higher irAEs that led to treatment discontinuation of a checkpoint inhibitor should be excluded. Subjects with irAEs below grade 3 that led to discontinuation should be discussed with the sponsor.
  - Subjects with a prior history of myositis, Guillain-Barré syndrome, or myasthenia gravis of any grade are excluded.
  - History of chronic liver disease or evidence of hepatic cirrhosis.
  - History of non-infectious pneumonitis that has required steroids, or currently has pneumonitis.
  - History of organ allograft (except for corneal transplant) or autologous or allogeneic bone marrow transplant, or stem cell rescue within 3 months prior to the first dose of GEN1044.
  - O Serious, non-healing wound, skin ulcer (of any grade), or bone fracture.
- Any history of intracerebral arteriovenous malformation, cerebral aneurysm, new (within the last 6 months) or symptomatic brain metastases or stroke. (Transient ischemic attack >1 month prior to screening is allowed.)
- Subjects with brain metastases must not be undergoing acute corticosteroid therapy or steroid taper. Chronic steroid therapy is acceptable provided that the dose is stable for the last 14 days prior to screening (≤10 mg prednisone daily or equivalent).
- Subjects with CNS symptoms should undergo a computed tomography (CT) scan or magnetic resonance imaging (MRI) of the brain to exclude new or progressive brain metastases. Spinal cord metastasis is acceptable. However, subjects with spinal cord compression should be excluded.
- Known past or current malignancy other than inclusion diagnosis, except for
  - o Cervical carcinoma of Stage 1B or less.
  - o Non-invasive basal cell or squamous cell skin carcinoma.
  - o Non-invasive, superficial bladder cancer.

	o Prostate cancer with a current PSA level <0.1 ng/mL.	
	○ Any curable cancer with a complete response (CR) of >2 years duration.	
	• Has a history of ≥ grade 3 allergic reactions to monoclonal antibody therapy as well as known or has known allergies, hypersensitivity, or intolerance to GEN1044 or its excipients.	
	• Is a woman who is pregnant or breast-feeding.	
IMP	GEN1044, IV administration	
Efficacy Assessments	Efficacy assessments will include radiological/imaging assessments, bone scans (as applicable), prostate-specific antigen (PSA) results (as applicable), and survival status.	
Safety Assessments	Safety assessments will include AEs, clinical laboratory assessments, physical examinations, vital signs, 12-lead electrocardiograms (ECGs), and ECOG-PS.	
Other Assessments	Other assessments will include the evaluation of PK and immunogenicity samples, and the evaluation of biomarkers in blood, tumor biopsy	
Statistics	During the Dose Escalation part of the trial, the DLT rates will be presented to the DEC by each DL cohort and per each period-specific dose level, following a BOIN approach. The RP2D will be based on the accumulated DLT data, taking the totality of data into account.	
	The primary endpoint in the Expansion cohorts is the ORR (ie, confirmed complete response or partial response per local review). Subjects eligible for an expansion cohort will be entered in a stage-wise fashion. For each stage, the "success" of the stage is predicted based on Bayesian methods given the ORR observed so far in the cohort. If the predictive probability of success is less than 10%, the cohort will not be further explored.	
	AEs and safety laboratory parameters will be presented using summary statistics.	
	Individual curves of concentration of GEN1044, including information on actual dose, will be presented for all subjects. PK parameters will be calculated based on non-compartmental methods.	
	Summaries of objective response, best overall tumor response and disease control will be presented.	
	PFS, OS and DOR will be summarized using survival analysis methods. The number of events may be small, and thereby limit use of the Kaplan-Meier methods to provide reliable information. In this case, descriptive statistics (eg, n, mean, standard deviation, median, minimum and maximum) will be presented.	
GCP Compliance	This trial will be conducted in compliance with the protocol, principles of the Declaration of Helsinki, International Council for Harmonisation Good Clinical Practice, ICH GCP E6(R2), and applicable regulatory requirements.	

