# 11.5.10.3 Duration of Response

Duration of response (DOR) only applies to subjects with a best overall response that is either confirmed CR or confirmed PR according to RECIST v1.1 based on tumor response data per local review. The start date is the date of first documented response of CR or PR (ie, the start date of response, not the date when response was confirmed), and the end date is defined as the date of the first documented progression or death due to any cause. Subjects continuing without progression or death due to underlying cancer will be censored at the date of their last adequate tumor assessment. In case of progression after  $\geq 2$  missed visits, censoring will be done at last adequate tumor assessment date.

DOR distribution will be estimated using the Kaplan-Meier method, and the survival curve, median and 95% CI of the median will be presented. If too few responders this analysis may be omitted. Individual subject data listings will be provided.

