# 11.6.8 Secondary Endpoint – Evaluation of Efficacy

# 11.6.8.1 Progression-free Survival

PFS is defined as the time from the date of C1D1 to the date of the first documented progression or death due to any cause. PFS will be assessed via local review according to RECIST v1.1 (Eisenhauer et al., 2009). PFS will be censored in accordance with Table C1 in Appendix C in the FDA Guidance for Industry: Clinical Trial Endpoints for the Approval of Non-small Cell Lung Cancer Drugs and Biologics (FDA-Guidance, 2015).

PFS will be analyzed in the FAS population. The PFS distribution will be estimated using the Kaplan-Meier method, and the Kaplan-Meier curves, medians and 95% CIs of the medians will be presented for each expansion cohort.

Version: 4.0

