#### 11.6.8.2 Overall Survival

OS is defined as the time from date of C1D1 to date of death due to any cause. If a subject is not known to have died, then OS will be censored at the latest date the subject was known to be alive (on or before the cut-off date).

OS will be analyzed in the FAS population. The OS distribution will be estimated using the Kaplan-Meier method, and the Kaplan-Meier curves, medians, first and third quartiles and 95% CIs of the medians will be presented for each expansion cohort.

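### The synopsis's few-events fallback to ordinary means and medians ignores censoring in PFS, OS and DOR, and conflicts with Section 11

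*Protocol*

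**What the plan says.** The Statistics entry of the synopsis (Protocol Section 1.1) starts from the usual position: "PFS, OS and DOR will be summarized using survival analysis methods". It then gives a reason to depart from it, "The number of events may be small, and thereby limit use of the Kaplan-Meier methods to provide reliable information", and says what follows: "In this case, descriptive statistics (eg, n, mean, standard deviation, median, minimum and maximum) will be presented". No number of events triggers the switch, and nothing is said about subjects without an event.

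Section 11 defines all three endpoints with censoring:
- OS (Section 11.6.8.2): "If a subject is not known to have died, then OS will be censored at the latest date the subject was known to be alive".
- PFS (Section 11.6.8.1): "PFS will be censored in accordance with Table C1 in Appendix C in the FDA Guidance for Industry".
- DOR (Section 11.5.10.3): responders without an event "will be censored at the date of their last adequate tumor assessment".

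The methods there do not repeat the fallback. For PFS, "The PFS distribution will be estimated using the Kaplan-Meier method", with no condition on the number of events, and OS is treated the same way. DOR is also Kaplan-Meier, with a different rule for sparse data: the analysis may be left out if there are too few responders, and individual listings are given.

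**The concern.** For PFS and OS, few events in a treated cohort means that most subjects are censored. An ordinary mean or median then has two possible inputs. If censored times are counted as though complete, the figure mainly measures how long subjects have been followed. If only event times are used, it describes the earliest failures. Neither estimates PFS or OS. The same holds for DOR while responders are still in response.

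Sparse events are a reason to report that a median has not been reached, which Kaplan-Meier already does. The fallback instead gives a definite number of months that looks like a result.

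The reads exposed to this were early ones. The expansion interim (Section 11.7) takes place once about 20 subjects have at least two reviewed scans, and DOR, PFS and OS are among the supplementary summaries the sponsor Safety Committee would see. The individual cohort analyses could also be early. In addition, the synopsis and Section 11 give different instructions for the same endpoints.

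**Working it through.** The plan states no event count, power or expected median for PFS, OS or DOR, so there is no figure of its own to reproduce.

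**Direction.** Let T be the true time and C the censoring time. The recorded time is min(T, C), which never exceeds T, so counting censored times as complete can only lower the mean and the median. Using event times only keeps subjects with T ≤ C. If censoring is independent of T, this favours short times, so it is also too low.

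**Size: inputs.**
- From the documents: two on-treatment scans, about 12 weeks (Section 4.3; the two-scan condition is also in Sections 11 and 11.7). That is 84 days / 30.4375 = 2.76 months, using the SAP's conversion in Section 5.3.
- Assumed: exponential times with true median m of 6, 8 or 12 months; follow-up uniform between a = 2.76 months and b = 6 or 9 months.

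**Formula.** With λ = ln 2 / m, the proportion of recorded times beyond t is exp(−λt) × G(t). G(t) = 1 up to a, and (b − t)/(b − a) from a to b. The ordinary median is the t at which this equals 0.5.

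**Example, m = 8, b = 6.** At t = 3.76: exp(−0.0866 × 3.76) = 0.722; G = (6 − 3.76)/3.24 = 0.691; product 0.50. The ordinary median is 3.8 months against a true 8, which is 47%. The event fraction is 31%. For exponential times the ordinary mean divided by the true mean equals the event fraction, so the mean is 0.31 × 11.5 = 3.6 months against 11.5.

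| True median (months) | Longest follow-up (months) | Events | Ordinary median (months) | Share of truth |
|---|---|---|---|---|
| 6 | 6 | 39% | 3.6 | 59% |
| 8 | 6 | 31% | 3.8 | 47% |
| 12 | 6 | 22% | 4.0 | 33% |
| 6 | 9 | 48% | 4.0 | 67% |
| 8 | 9 | 39% | 4.4 | 55% |
| 12 | 9 | 28% | 4.9 | 41% |

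With 6 months' maximum follow-up, doubling the true median from 6 to 12 months moves the ordinary median only from 3.6 to 4.0.

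**Second check by simulation.** 4,000 runs per scenario, n = 40, exponential times with true medians of 3, 6 or 12 months, uniform accrual over 6 or 12 months, and minimum follow-up from 0.5 to 24 months. Ratios to the true median:

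| Events | All times, ordinary median | Event times only, median |
|---|---|---|
| 18% | 0.25 | 0.15 |
| 29–32% | 0.42 | 0.23–0.28 |
| 49% | 0.69–0.70 | 0.41 |
| 73% | 0.97 | 0.66 |
| 97% | 1.02 | 0.97 |

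n = 20 shows the same pattern. The error is greatest where events are fewest and almost disappears when nearly everyone has had an event.

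**Kaplan-Meier on the same data** (n = 40, true median 6 months). At 49% events the estimated median is 6.0 months and is reached in 87% of runs, against an ordinary median of 4.2. At 32% events it is reached in 48% of runs and is otherwise reported as not reached, against an ordinary median of 2.5.

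**The case against.** The strongest reply is that nothing now depends on the sentence. PFS and OS belong only to the expansion part (Protocol Tables 9 and 10). Enrolment was stopped (SAP 1.2), the expansion analyses were deleted because no expansion data were collected (SAP 2.2), and efficacy is listed rather than summarised (SAP 2.1). This stands: no table in the abbreviated CSR is affected. It does not make the protocol's rule correct.

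Section 11 can also be said to contain the right methods already. For PFS and OS that is true, and it makes the repair easy. But the synopsis states a rule of its own, so the two places must be reconciled.

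For DOR, few events may simply mean few responders. At a 10% response rate, 40 subjects give 4 responders; if all have progressed, nothing is censored and a median and range are valid. This stands, so the DOR point is limited to responders who are still ongoing.

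Some stronger readings are tempting but not supported:
- **Kaplan-Meier is dropped.** Replacement is the natural sense of the sentence, but the text does not expressly say so.
- **A larger bias.** If follow-up starts at zero and runs to 4 to 9 months, the ordinary median is 15% to 47% of the truth. The two-scan condition rules out such short follow-up for subjects still on treatment.
- **Cohorts ranked by enrolment date.** Nothing in the protocol ranks cohorts on PFS, OS or DOR. The futility and success rules use ORR, and no formal hypotheses are stated. What can be said is that such medians would partly reflect length of follow-up.

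**Conclusion.** The synopsis rule is wrong as written. Applied when events are few, it yields figures that understate PFS and OS, and DOR while responders are ongoing. It also contradicts Section 11. Under the stated assumptions the ordinary median is about 33% to 67% of the true median. The upper end comes from a scenario with 48% events, which many would not call few; the lower end has 22%. These sizes depend on the assumed exponential times, medians and follow-up. The direction needs no distributional assumption when censored times are counted as complete, and only independent censoring when event times alone are used.

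The endpoints are secondary and supplementary to ORR at the interim. A reader might infer that the reported results of this trial are biased; the SAP shows that they are not, because these summaries are no longer produced. The correction concerns the protocol text, and any later protocol that reuses it.

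**What to change.** Delete the fallback sentence from the synopsis and align the entry with Section 11. When events are few:
- keep the Kaplan-Meier presentation;
- give the numbers of events and of censored subjects;
- show the median as not reached where that is the case;
- list individual times with a censoring flag;
- for DOR, keep the existing option to omit the analysis when responders are too few.

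The deletion costs one sentence. The event and censoring counts and the flag are small additions to outputs already planned. Event-free rates at fixed times, follow-up by reverse Kaplan-Meier and swimmer plots would be useful, but Section 11 does not plan them; they are optional extra work and not needed to correct the error. The abbreviated CSR needs no change.

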#### 1.2 Schema

Figure 1 Trial Design

AE = adverse event; DL = dose level, DLT = dose-limiting toxicity, RP2D = recommended phase 2 dose.

Version: 4.0

#### 1.3 Schedule of Activities

Table 1 through Table 8 list all of the assessments and indicate with an "X" the evaluations performed by visit.

- Table 1: Visit Evaluation Schedule Dose Escalation Part
- Table 2: PK, ADA and ECG Sampling Dose Escalation Part
- Table 3: Vital Signs Dose Escalation Part
- Table 4: Biomarker Table Dose Escalation Part
- Table 5: Visit Evaluation Schedule Expansion Part
- Table 6: PK, ADA and ECG Sampling Expansion Part
- Table 7: Vital Signs Expansion Part
- Table 8: Biomarker Table Expansion Part

In addition to the fixed visits, it may be necessary to perform some of the assessments at unscheduled time points if deemed clinically necessary by the investigator. All data obtained from these assessments must be supported in the subject's source documentation.

Document Number: TMF-34513

**Table 1** Visit Evaluation Schedule – Dose Escalation Part

Treatment Cycle (C)	Notes	Section Reference	Screening					Cycl	e 1							Cycle	2		
Day (d)/Week (wk)			≤ 28d prior to C1 (1d)	1d	2d	4d	8d	9d	11d	15d	16d	18d	1d	2d	4d	8d	9d	11d	15d
Visit window							+1d			+1d			+2d			+2d			+2d
Informed Consent		13.2.3	X																
Eligibility Criteria		5.1, 5.2	X																
Demographics		9.1.1	X																
Medical History		9.1.2 to 9.1.5	X																
Body weight		9.3.2	X																
Physical Examination	After Screening, perform exam only as indicated by subject's symptoms, AEs, or findings as determined by investigator.	9.3.1	X	X			X			X			X			X			X
Vital Signs	See Table 3 for GEN1044 dosing days. At Unscheduled visit, perform only as indicated by subject's symptoms, AEs, or findings as determined by investigator.	9.3.3	X	X			X			X			X			X			X
ICE Score Assessment	See Table 18.	10.4.2	X	X			X			X			X						
ECG	See Table 2	9.3.4	X																
Radiological Exam/Tumor Imaging	Imaging is calendar based. On-treatment imaging every 6 wks (±7d) for the first 36 wks (calculated from C1D1), then every 12 wks (±7d) until PD, start of new anticancer therapy, consent withdrawn, or death, whichever occurs first.	9.2.1	Xª																
Whole-body Bone Scan	Subjects with prostate cancer. Ontreatment scans every 6 wks (±7d) (or longer per local standards) for the first 24 wks(calculated from C1D1), then every 12 wks (±7d) until PD, start of new anticancer therapy, consent withdrawn, or death, whichever occurs first.	9.2.1	X																
ECOG-PS	Do not perform C1D1 ECOG-PS if within 5 days of Screening ECOG-PS. C1D1 ECOG-PS must be within 0-1 or subject cannot receive GEN1044. At Unscheduled visit, only if relevant.	9.3.5	X	X									X						

Document Number: TMF-34513

Treatment Cycle (C)	Notes	Section Reference	Screening					Cyclo	e 1							Cycle	2		
Day (d)/Week (wk)			≤ 28d prior to C1 (1d)	1d	2d	4d	8d	9d	11d	15d	16d	18d	1d	2d	4d	8d	9d	11d	15d
Visit window							+1d			+1d			+2d			+2d			+2d
Adverse Events	See footnote "b." Report all AEs from first GEN1044 dose (C1D1) until 30 days after the last GEN1044 dose (ie, Safety Follow-up visit). After SFU only report suspected GEN1044-related SAEs.	10.1, 10.2	Xb	X	X	X	X	X	X	X	X	X	X	X	X	X		X	X
Concomitant Medication		6.5, 9.1.4	X	X	X	X	X	X	X	X	X	X	X	X	X	X		X	X
Premedication with Corticosteroids, Antihistamines and Antipyretics	Premedication is mandatory 30 to 120 minutes prior to first 3 administrations of GEN1044.	6.2, 6.5		X			X			X									
GEN1044 Administration g		6.3, 6.6		X			X			X			X			X			X
LABORATORY AS	SSESSMENTS																		
Hematology	At Unscheduled visit, only if relevant.	9.4	Xc	X	X	X	X	X	X	X	X	X	X			X			X
Biochemistry	At Unscheduled visit, only if relevant.	9.4	Xc	X	X	X	X	X	X	X	X	X	X		X	X		X	X
Coagulation factors	At Unscheduled visit, only if relevant.	9.4	Xc										X						
Urinalysis	At Unscheduled visit, only if relevant.	9.4	X c																
Pregnancy test	At Unscheduled visit, only if relevant.	9.4	X c																
Hepatitis B	At Unscheduled visit, only if relevant.	9.4	Xc																
T3, T4	At Unscheduled visit, only if relevant.	9.4	Xc																
PK/ADA sampling	See Table 2	9.5, 9.6																	
Tumor biopsy, biomarkers	See Table 8	9.7																	
PSA	Subjects with prostate cancer; central lab	9.2.2	Xc	X									X						
Serum testosterone	Subjects with prostate cancer; central lab	9.4.1	Xc																

Document Number: TMF-34513

 Table 1
 Visit Evaluation Schedule - Dose Escalation Part (Continued)

Treatment Cycle (C)	Notes	Section Reference	Cycle	3 to C	ycle 4	Cyc	le 5 to	PDf	Treatment Discontin- uation visit	Safety Follow-up visit	Survival Follow-up	Unscheduled
Day (d)/Week (wk)			1d	8d	15d	1d	8d	15d	-	30d after last dose	Every 12 wk after last dose	
Visit window			+3d	+1d	+3d	+3d	+3d	+3d		+14d	+7d	
Body weight		9.3.2							X			
Physical Examination	After Screening, perform exam only as indicated by subject's symptoms, AEs, or findings as determined by investigator.	9.3.1	X	X	X	X	Xf	Xf	X	X		X
Vital Signs	See Table 3 for GEN1044 dosing days. At Unscheduled visit, perform only as indicated by subject's symptoms, AEs, or findings as determined by investigator.	9.3.3	X	X	X	X	Xf	Xf	X	X		Х
ECG	See Table 2	9.3.4										
Radiological Exam/Tumor Imaging	Imaging is calendar based. On-treatment imaging every 6 wks (±7d) for the first 36 wks (calculated from C1D1), then every 12 wks (±7d) until PD, start of new anti-cancer therapy, consent withdrawn, or death, whichever occurs first.	9.2.1							$X^d$			
Whole-body Bone Scan	Subjects with prostate cancer. Ontreatment scans every 6 wks (+7d) (or longer per local standards) for the first 24 weeks (calculated from C1D1), then every 12 weeks (±7d) until PD, start of new anti-cancer therapy, consent withdrawn, or death, whichever occurs first.	9.2.1							X d			
ECOG-PS	At Unscheduled visit, only if relevant.	9.3.5	X			X			X	X		X
Adverse Events	See footnote "b." Report all AEs from first GEN1044 dose (C1D1) until 30 days after the last GEN1044 dose (ie, Safety Follow-up visit). After SFU, only report suspected GEN1044-related SAEs.	10.1, 10.2	X	X	X	X	Xf	X f	X	X	X	X
Concomitant Medication		6.5, 9.1.4	X	X	X	X	Xf	Xf	X	X		X
Premedication with Corti- costeroids, Antihistamines and Antipyretics	Premedication is mandatory 30 to 120 min prior to first 3 administrations of GEN1044	6.2, 6.5										
GEN1044 Administration		6.3, 6.6	X	X	X	X						

Document Number: TMF-34513

Treatment Cycle (C)	Notes	Section Reference	Cycle	3 to C	ycle 4	Cyc	le 5 to	PDf	Treatment Discontin- uation visit	Safety Follow-up visit	Survival Follow-up	Unscheduled
Day (d)/Week (wk)			1d	8d	15d	1d	8d	15d	-	30d after last dose	Every 12 wk after last dose	
Visit window			+3d	+1d	+3d	+3d	+3d	+3d		+14d	+7d	
End of treatment	Perform Treatment Discontinuation visit as soon as possible after permanent GEN1044 discontinuation	8.1, 8.1.1							X			
Inquire if any new anti-cancer treatment		8.1.2							X	X	X	
Survival follow-up	Perform survival follow-up by telephone, email, or visit.	8.1.3, 9.2.3									X	
LABORATORY ASSESS	MENTS											
Hematology	At Unscheduled visit, only if relevant.	9.4	Xe			Xe			Xe	$X^e$		X
Biochemistry	At Unscheduled visit, only if relevant.	9.4	Xe			Xe			Xe	Xe		X
Coagulation factors	At Unscheduled visit, only if relevant.	9.4							Xe			X
Urinalysis	At Unscheduled visit, only if relevant.	9.4	Xe			Xe			Xe			X
Pregnancy test	At Unscheduled visit, only if relevant.	9.4	Xe			Xe			Xe			X
Hepatitis B	At Unscheduled visit, only if relevant.	9.4										X
T3, T4	At Unscheduled visit, only if relevant.	9.4								-		X
PK/ADA sampling	See Table 2	9.5, 9.6										
Tumor biopsy, biomarkers	See Table 4	9.7										
PSA	Subjects with prostate cancer; central lab	9.2.2	Xe			X			X			X
Serum testosterone	Subjects with prostate cancer; central lab	9.4.1								/		

- a. During Screening: All subjects will have a contrast CT of the chest/abdomen/pelvis; a non-contrast CT of chest and MRI of abdomen/pelvis, or chest x-ray as applicable for their respective tumor type. For subjects with SCCHN, head and neck imaging is also required; imaging of the pelvis is strongly recommended but not required. If a CT-scan or MRI has been performed within 28 days prior to visit Cycle 1 Day 1 as part of standard procedure, it is acceptable as a screening scan for the trial. If there is suggestion of brain metastases/tumors, a CT-scan or MRI of the head and neck will be performed within 28 days prior to the Cycle 1 Day 1 visit. A bone scan is required for subjects with prostate cancer.
- b. Medical conditions occurring after ICF is signed and prior to first GEN1044 dose should only be reported as AEs if they were assessed by the investigator to be caused by a protocol-mandated procedure (ie, tumor biopsy and/or CT scan), including washout or discontinuation of prior medications. Any medical history that worsens after the first dose of GEN1044 will be recorded as an AE. If the subject initiates new anti-cancer therapy within 30 days of the last dose of GEN1044, the SFU visit should be performed prior to starting new anti-cancer therapy. SAEs still ongoing after Safety Follow-up visit should be followed on a regular basis according to the investigator's clinical judgment until the event has been resolved or until the investigator assesses it as chronic and all queries have been resolved.
- c. Obtain screening labs within 7 days of Cycle 1 Day 1 (exception: hepatitis B sample may be obtained earlier). Central lab: serum (beta-hCG) pregnancy, hepatitis B, T3, T4, serum testosterone, PSA; local lab: hematology, biochemistry, coagulation factors and urinalysis.
- d. Radiological exam/tumor imaging and if applicable, bone scan, at Treatment Discontinuation visit unless performed within 28 days of last scheduled exam.
- $e. \ Starting \ with \ C3, obtain \ labs \leq 3 \ days \ before \ D1. \ Central \ lab: \ PSA; \ local \ lab: \ hematology, \ biochemistry, \ coagulation \ factors, \ urine \ pregnancy \ test, \ and \ urinalysis.$
- f. Only collect during C5.

Document Number: TMF-34513

 Table 2
 PK, ADA and ECG Sampling – Dose Escalation Part

Treatment Cycle (C)	Notes	Section Reference	Screening					Cycle	1							Cycle	2		
Day (d)/Week (wk)			≤ 28d prior to C1 (1d)	1d	2d	4d	8d	9d	11d	15d	16d	18d	1d	2d	4d	8d	9d	11d	15d
Visit window							+1d			+1d			+2d			+2d			+2d
PK SAMPLING		9.5																	
Before Infusion (on infusion days)				X			X			X			X			X			X
End of infusion (+15 min)				X			X			X			X			X			X
End of infusion +2 hr (±15 min)										X			X						
End of infusion +6 hr (+3 hr)				X			X			X			X						
24 hr sample post end of infusion	Collect C1D2, C1D9, and C1D16 PK sample 24 ±2 hr after end of D1, D8 and D15 infusion, respectively. Collect C2D2 sample 24 ±2 hr after the end of C2D1 infusion.				X			X			X			X					
72 hr sample post end of infusion	Collect C1D4 and C1D18 PK sample 72 ±24 hr after end of D1 and D15 infusion, respectively. Collect C2D4 sample 72 ±24 hr after the end of C2D1 infusion.					X						X			X				
ADA SAMPLING		9.6																	
Before Infusion (on infusion days)				X									X						
ECGs		9.3.4																	
Before Infusion (on infusion days)	Triplicate ECGs, performed within 20 minutes but at least 2 min apart		X	X			X												
End of infusion (+15 min)	Triplicate ECGs, performed within 20 minutes but at least 2 min apart			X			X												

Document Number: TMF-34513

Table 2 PK, ADA, and ECG Sampling - Dose Escalation Part (Continued)

Treatment Cycle (C)	Notes	Section Reference	Cycl	e 3 to (	Cycle	4			Cyc	le 5 to	o PD		Treatment Discontin- uation visit	Safety Follow- up visit	Survival Follow- up	Unsched- uled
Day (d)/ Week (wk)			1d	8d	9d	11d	15d	1d	2d	4d	8d	15d	-	30d after last dose	Every 12 wk after last dose	
Visit window			+3d	+1d			+3d	+3d			+3d	+3d		+14d	+7d	
PK SAMPLING		9.5														
Before Infusion (on infusion days)	Optional at Unscheduled visits		Xa	Xb			Xb	Xª					X	X		X
End of infusion (+15 min)			$X^a$	X b			X b	Xª								
End of infusion +2 hr (±15 min)				X b				Xc								
End of infusion +6 hr (+3 hr)				Xb												
24 hr sample post end of infusion	C5 only: PK sample 24±2 hr after end of C5D1 infusion (ie, on C5D2)				Xb				Xc							
72 hr sample post end of infusion	C5 only: PK sample 72±24 hr after end of C5D1 infusion (ie, on C5D4)					Xb				Xc						
168 hr sample post end of infusion	C5 only: Collect PK sample 168+72 hr after end of C5D1 infusion (ie, on C5D8)										X c					
336 hr sample post end of infusion	C5 only: Collect PK sample 336+72 hr after end of C5D1 infusion (ie, on C5D15)											Xc				
AD A CAMPINE		0.6														
ADA SAMPLING		9.6														
Before Infusion (on infusion days)	Optional at Unscheduled visits		$X^d$					$X^{d}$					X	X		X

Document Number: TMF-34513

Treatment Cycle (C)	Notes	Section Reference	Cycl	e 3 to (	Cycle	4			Сус	ele 5 t	o PD		Treatment Discontin- uation visit	Safety Follow- up visit	Survival Follow- up	Unsched- uled
Day (d)/ Week (wk)			1d	8d	9d	11d	15d	1d	2d	4d	8d	15d	-	30d after last dose	Every 12 wk after last dose	
Visit window			+3d	+1d			+3d	+3d			+3d	+3d		+14d	+7d	
ECGs		9.3.4														
Before Infusion (on infusion days)	Optional at Unscheduled visits; if performed, ECG in triplicate, performed within 20 minutes but at least 2 min apart		Xe													X
End of infusion (+15 min)			Xe													

a. Collect PK samples at C3D1, C4D1, C5D1, C6D1, C7D1, then every 4 cycles thereafter on Day 1.
b. Only collect during C3.
c. Only collect during C5. 

d. Collect ADA samples at C3D1, C5D1, C7D1, then every 4 cycles thereafter on Day 1.
e. Only to be collected for C3D1, not remaining cycles. 

Document Number: TMF-34513

Version: 4.0

